CRO	Contract Research Organisation
СТА	Clinical Trial Authorisation
DSMC	Dosing and Safety Monitoring Committee
EC	European Commission
ED	Emergency Department
EMEA	European Medicines Agency
EU	European Union
EUCTD	European Clinical Trials Directive
EudraCT	European Union Drug Regulating Authorities Clinical Trials
GAfREC	Governance Arrangements for NHS Research Ethics Committees
GCP	Good Clinical Practice
GMP	Good Manufacturing Practice
IB	Investigator Brochure
ICF	Informed Consent Form
IMP	Investigational Medicinal Product
IMPD	Investigational Medicinal Product Dossier
ISRCTN	International Standard Randomised Controlled Trial Number
JRMO	Joint Research Management Office
MA	Marketing Authorisation
MS	Member State
NEWS	National Early Warning Score
NICE	National Institute for Health and Care Excellence
NHS	National Health Service
SCD	Sickle cell disease
VOE	Veno-occlusive pain episode

3. Signature page

Date:

Chief Investigator Agreement

The study as detailed within this research protocol will be conducted in accordance with the principles of Good Clinical Practice, the UK Policy Framework for Health and Social Care Research, and the Declaration of Helsinki and any other applicable regulations. I delegate responsibility for the statistical analysis and oversight to a qualified statistician (see declaration below).

Chief Investigator name: _[name]
Signature:	
Date:	
Statistician's Agreement	
The study as detailed within this rewith the current UK Policy Framework Medical Association Declaration of - Statistical principles for Clinical Tr	esearch protocol will be conducted in accordance ork for Health and Social Care Research, the World Helsinki (1996), principles of ICH E6-GCP, ICH E9 ials and ICH E10 - Choice of Control Groups.
I take responsibility for ensuring the take responsibility for statistical ana	e statistical work in this protocol is accurate, and I lysis and oversight in this study.
Statistician's name:	
Signature:	

4. Summary and synopsis

Short title	Sickle Cell Acute Pathway Evaluation (SCAPE 2)								
Methodology	Multi-centre, open, randomised controlled trial with patients								
	individually randomised to Emergency Department (ED) or								
	Specialist Ambulatory Care Unit (ACU) when presenting to								
	hospital with acute painful crisis of sickle cell disease								
	(SCD)								
Research sites	NHS hospitals covering moderate or high prevalence sickle								
	cell populations, and providing both ED and ACU								
Objectives / aims	To determine whether, in an adult sickle cell disease								
	population, the acute painful crisis is better managed in a								
	dedicated specialist ambulatory care unit compared wit								
	standard care in a hospital emergency department.								
	Outcome measures will include sequential pain scores								
	measured using visual analogue scale, time to first								
	analgesia, opioid consumption, rate of hospital admission,								
	time to readiness for discharge, patient health-related								
	quality of life, patient satisfaction and cost-effectiveness.								
Number of	228 patient episodes (114 per group).								
participants									
Inclusion and	Inclusion								
exclusion criteria	1. Male or female participant with SCD (any genotype)								
	2. Age 16 or older								
	3. Registered in the trial centre sickle cell service with								
	a pre-agreed personal pain management protocol								
	upleaded on their electronic patient record								
	uploaded on their electronic patient record								
	4. At least one attendance at hospital with acute pain								
	during the past 2 years								
	Able and willing to give informed consent								
	6. Uncomplicated acute painful crisis requiring acute								
	hospital treatment								
	7. Pain score 5 or more on a numeric rating 0-10 scale								
	8. Confirmed signed consent form								
	Exclusion								
	1. Participants who are pregnant and more than 16								
	weeks' gestation								
	2. More than 10 hospital attendances for acute pain								
	management in the past 12 months								
	3. Participant already treated for two pain episodes								
	within the SCAPE-2 trial protocol								
	4. Participant has been treated for a pain episode on								
	the trial protocol within 28 days								
	5 The ACI is open for less than 6 hours from time of								
	nrecontation								
	o. Additional sickle cell complication as assessed at								
	telephone triage or on arrival by specialist medical								
	and/or nursing staff:								
	a. Acute chest syndrome								

	b. Acute stroke
	c. Priapism
	d. Sepsis
	 e. Observations Temp >38.5 degrees, oxygen saturations <94%
	f. Any other medical issue at the trial team discretion
Statistical methodology and analysis (if applicable)	The primary outcome of pain score over the 6 hours following presentation will be compared between randomised groups using a mixed effects regression model accounting for correlation between repeated observations within participants. Analyses will be done on an intention-to-treat basis.
Study duration	36 months

5. Introduction

5.1 Background

The acute painful crisis (APC) is the most common complication of sickle cell disease (SCD). These episodes of pain are unpredictable in onset and duration and can progress to life-threatening complications, including acute chest syndrome, acute fat embolism syndrome and multi-organ failure. Severe APC may require treatment in hospital with strong opioid analgesic drugs, combined with additional supportive care measures. Careful monitoring of pain score and vital signs is essential to ensure adequate pain control, avoidance of adverse effects of analgesic drugs, and prompt intervention to manage complications¹.

Guidelines for APC management have been produced over the past two decades gathering evidence from published studies, expert opinion, and patient perspective. Unfortunately, reports from multiple sources indicate that guidelines are often not followed. Furthermore, acute care in emergency departments and on acute medical wards is suboptimal, leading to patient dissatisfaction, anxiety, and sometimes to avoidable harm. In the UK, this was recently highlighted in the report 'No one's listening' prepared by the All Party Parliamentary Group on Sickle Cell Disease and Thalassaemia (APPG)². The report identified a wide range of deficiencies in services, and highlighted that the National Health Service (NHS) core values of respect and dignity, compassionate care, quality, and inclusion are not being consistently applied to people living with SCD.

For severe acute pain which cannot be managed at home, the hospital emergency department (ED) is the default location for health care intervention. This is because ED is open 24 hours per day and provides access to trained medical, nursing and allied health care professional staff who can provide urgent assessment and treatment. Challenges with ED care are well-described and generally difficult to resolve. They include lack of continuity and connection with the patient's SCD treatment team, delays in triage and assessment, reassessment, and repeat analgesia dosing. The environment is often overcrowded, noisy and stressful, and does not encourage biofeedback techniques for self-management of pain, such as relaxation and distraction. Furthermore, problematic staffing attitudes in the non-specialist setting can generate a feeling of stigma and discrimination. Patients may be labelled as drug seeking, obstructive or difficult.

Potential alternatives to current ED care include specialised units providing care in an alternative hospital-based setting. These are variously described as ambulatory units, day care units or infusion centres. For the purposes of this study we refer to them as Specialist Hospital-based Ambulatory Care Units (ACUs). The ASH guideline specified that patients on these units should be managed by a team specialised in acute SCD pain management, and should be located in a hospital with easy access to acute and intensive care facilities, recognising that occasionally patients present with acute pain together with life-threatening complications including acute chest syndrome and sepsis. This type of care provision is generally available during working hours only (Monday to Friday, 9am to 5 pm), although there are some examples of extended opening hours.^{3, 4}. The unit could be entirely dedicated to SCD, or alternatively, with smaller patient populations or insufficient dedicated staff and space, the service could be embedded in a larger multi-specialty unit, such as a hospital-based haemato-oncology unit.^{3, 5}

Currently, there are no randomised studies comparing standard ED care with ACU's, and relatively few observational studies, which are predominantly from a United States health care perspective. Reports in the 1990's from Montefiore Medical Centre, New York, USA⁶, and the Day Centre at Birmingham City Hospital, UK⁷, demonstrated satisfactory pain control, and reduction in hospital admissions, leading to significant cost savings for the service. These finding have subsequently been replicated in other centres such as an infusion clinic at Johns Hopkins Medical Centre and in the paediatric setting^{3, 4, 8, 9}. A report from a day care unit in Jamaica where the unit was not located in a hospital setting highlighted the potential for harm. Fatal events were reported in a small number of patients who had been discharged home, with causes of death including acute chest syndrome and sepsis.¹⁰

More recently, Lanzkrom et al have published a study attempting to compare outcomes in infusion centres (IC) with ED³. The ESCAPED (Examining Sickle Cell Acute Pain in the Emergency Versus Day Hospital) study was a prospective observational study in four US cities. The investigators considered that randomly assigning to ED or IC was not possible because patients are reluctant to be assigned to ED-only care, and also because of the practical challenges of randomising during an acute VOC event. Patients would be preferentially treated in an IC during working hours, but for various reasons (low staffing, non-availability of beds, additional complications) might be allocated to care in ED. In order to account for potential bias in the type of patient and presentation being treated in IC or ED, a propensity score was applied to each event. Patients treated in an IC received parenteral pain medication substantially faster than those seen in the ED, were more likely to have their pain reassessed 30 minutes after their initial dose of parenteral medication and substantially less likely to be hospitalized than those who received care in an ED. A subsequent health economic analysis of this study suggested large savings in medical and societal costs in the US, largely driven by reduction in hospital admissions in those attending IC.¹¹

One potential concern is whether opening an acute care facility might encourage patients to attend hospital for pain control rather than managing their pain at home, and this could increase hospital admissions and chronic opioid exposure. This might need to be managed by restricting access to facilities for high frequency service users. It is also not clear how the facility would be made available to patients in low-prevalence areas, with more limited specialist service provision. One proposed solution is provision of a centralised Hyper-acute Unit providing acute care for all service users in the region, and open 24 hours a day.¹² This type of unit may be suitable for service users who are local to the unit, but might entail prolonged travel for those living in other parts of the region, and might substantially increase the volume of patients requiring care and potentially hospital admission, in the hospital where the unit is hosted.

Although SCD-specific acute care facilities appear to have advantages over the ED, they are not yet standard of care and there are challenges and significant resource implications for health care providers in setting up these services. There are gaps in the existing data, which is largely retrospective and observational, and both the NICE and ASH guidelines have recommended further research in this area to compare clinical outcomes, patient satisfaction and health economic implications. A true randomised trial comparing outcomes in the ED and ambulatory care unit, including different types and size of service complemented by health economic evaluation and assessment of patient satisfaction might resolve some of the uncertainties and enable progress in optimizing care pathways.

This study aims to address these uncertainties in a prospective, randomised multicentre trial of adults with SCD presenting with acute sickle pain. The design of the study takes into account experience in conducting clinical trials in APC reviewed in a number of previous guidelines and reviews^{1, 13-17}, as well as the experience in the NHS setting in a dose finding and feasibility study for an oral opioid protocol, conducted at The Royal London Hospital between 2015 and 2018 (SCAPE 1)¹⁸. For this study protocol, SCAPE 2, multiple NHS hospitals which are able to provide both ED and ambulatory care will be involved, and patients will be allocated treatment location on arrival in hospital after telephone assessment and triage and randomisation prior to arrival. Outcomes will include a primary end point of reduction in pain score, as well as opioid usage, admission rate, patient satisfaction and health economic assessment.

5.2 Rationale

The aim of this study is to build on current evidence summarised above, by conducting a trial to make a direct comparison of two care pathways currently available in the NHS for hospital management of acute sickle pain to establish the clinical and cost-effectiveness of an ambulatory care unit in comparison with current emergency department care in NHS institutions.

Current emergency department care often fails to meet national standards, and patient experience is often poor with significant variation in care across the NHS. An improved care pathway is needed, and there is data from retrospective and prospective nonrandomised studies indicating better outcomes with ambulatory care units compared to current ED care. These have largely been from the USA health care perspective and results may not be directly applicable to the NHS in England. There has never been a randomised study comparing ED and ambulatory care, and the need for well conducted randomised studies in this area have been highlighted in both the NICE and ASH guidelines on sickle pain management.

Although it seems likely that ambulatory care would be preferred by patients, it is not clear how much difference may be achieved in clinical outcomes of value to the patient, such as reduction in pain, in patient-reported quality of life, and in health care metrics, such as probability of being admitted to hospital rather than discharged home, and bed days spent in hospital for those admitted. These metrics would inform whether investing in setting up ambulatory care represents improved patient-centred outcome.

The All Party Parliamentary Group on Sickle Cell Disease and Thalassaemia report 'No One's Listening' summarised experiences and opinions from health care professionals, patients and families concerning deficiencies in NHS care for acute sickle pain. One recommendation of this report was to commission work on clinical trial design to address deficiencies in evidence of effective interventions. The NHS Race and Health Observatory, an independent organization, set up to explore ethnic inequalities in healthcare and to provide recommendations to inform policymaking and facilitate change, subsequently invited applications for a grant to develop a clinical trial addressing these deficiencies. This tender was awarded to the group developing the current protocol. The core of this group consisted of members of the National Sickle Pain Group, which had been supported by the NHS England Clinical Reference Group for specialised commissioning of haemoglobin disorders, and included a range of health care professionals and patient representatives. The patient representative for this project was delegated by the Sickle Cell Society and was involved in all stages of protocol development.

The protocol development included a national workshop held in May 2023, during which relevant literature was reviewed, care models in the USA were presented, and potential trial designs were discussed. The workshop was attended by health care professionals, health service managers and commissioners, patients, carers and representatives of the Sickle Cell Society.

By undertaking the current study, emergency department and haemoglobinopathy services in NHS institutions will become more engaged in quality improvement regarding acute pain management in sickle cell disease. The study will foster a more uniform approach to acute pain management across the NHS. The proposal to study the implementation of individual pain protocols by dedicated staff in two different acute settings will help to embed two vital elements of care (individual protocols and dedicated sickle pain specialist nurses) into routine care.

In addition, the trial will answer important questions for quality of care and the costeffectiveness of ambulatory care units such as:

-Can hospital admissions be avoided?

-Can existing NHS quality standards around acute sickle pain management be better achieved?

-Can patient quality of life and satisfaction be improved?

-Can acute care be improved with reduced health economic impact on the NHS?

6. Study objectives

6.1 Primary objective

Is acute sickle cell pain better managed in a specialist ambulatory care unit (ACU) than in ED?

6.2 Secondary objective

Is patient satisfaction improved in a specialist ambulatory care unit compared to ED?

Is management in a specialised ambulatory care unit cost-effective compared to ED?

This trial will also contribute to developing a network of NHS hospital-based clinical trials centres where a series of trials can be undertaken to study further interventions aimed at improving clinical care and patient experience in managing acute sickle pain.

6.3 Primary endpoint

• Reduction in pain score during the first 6 hours after presentation to ED and ACU using a 0-10 numeric rating scale.

6.4 Secondary endpoints

- Time to first analgesia, defined as time from presentation in ACU or ED to first dose of opioid analgesia administered. (For subjects given parenteral opioid prior to arrival in care unit, e.g. in ambulance, timing will start from one hour after parenteral analgesia given in ambulance, even if subject presents less than one hour after analgesia given in ambulance)
- Adherence to NICE guideline in safety observations (defined as proportion of hourly safety observations (respiratory rate, sedation score) taken within first 6 hours (+/- 30 mins)
- Adherence to care plan in analgesia doses (defined as proportion of analgesia doses given according to protocol within first 6 hours (+/- 30 minutes)
- Fit for discharge by 6 hours after first analgesia (defined as pain score 5 or less for at least 2 consecutive hourly assessments; no requirement for parenteral opioid for at least 2 hours and acceptable oral analgesia protocol available for use at home, NEWS score green for >2 hours, patient able to self-administer oral medication, patient mobile. All the above assessed by physician and agreed with patient)
- Time from first analgesia to fit for discharge (defined as pain score 5 or less for at least 2 consecutive assessments; no requirement for parenteral opioid for at least 2 hours and acceptable oral analgesia protocol available for use at home, NEWS score green for >2 hours, patient able to self-administer oral medication, patient mobile. All the above assessed by physician and patient).
- Cumulative dose of morphine or equivalent opioids in first 6 hours and first 24 hours
- Proportion admitted to hospital from ACU or ED
- Length of hospital stay (for those admitted to hospital), length of hospital stay Patient satisfaction with care assessed using SCAPE questionnaire 14 and 28 days after discharge
- Health economic analyses of comparative patient health-related quality of life, costs and cost-effectiveness of ACU versus ED care from the perspective/s of health and social care (NHS and PSS) and, separately, wider society
 - Costs at 28 days post-randomisation
 - QALY at 28 days post-randomisation
 - Incremental cost-effectiveness ratio

7. Study population

Eligible participants will be selected from local registers of patients attending sickle cell services which are participating in the study. Patients will be informed about the study during out-patient appointments, after acute hospital attendances or by telephone call by a member of the clinical care team and informed about the study through written and verbal information.

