9.4 Randomization (See trial flow chart, Appendix, part 2 and 3)

Randomization will be done over the phone when a pre-consented subject calls the local trial centre with symptoms of APC. The procedures to be done by the trial nurse at the local trial centre to confirm consent and eligibility are listed in Section 9.2.3.

- 1. Verbal confirmation of consent and checking trial registration number
- 2. Confirming eligibility of APC using APC triage algorithm
- 3. Confirming trial eligibility against inclusion and exclusion criteria

If eligible for randomization, the local trial centre will next confirm the following

- 1. Both ED and ACU are available and resourced for treating the trial patient
- 2. Timing will permit 6 hours of treatment on ACU.

Once these items have been confirmed, randomization will be carried out by the local clinical trial nurse using a Queen Mary University of London Pragmatic Clinical Trials Unit dedicated online randomisation system. Participants will be randomised in a 1:1 ratio to the ambulatory care unit or hospital emergency department, stratifying by recruiting site, previous history of APC and age.

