9.5 Schedule of Treatment

Routine management of APC and of complications of APC should follow standard of care at the local trial centre. This includes selection of analgesic drugs, doses and route of administration, non-opioid analgesia and non-pharmacological treatments to manage pain. Care during the APC will be given by the standard care team rather than the trial team.

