11.1 Sample size

The target sample size is 228 patient episodes (114 per group). This provides 90% power (with 2-sided α =0.05) to detect a mean difference between ambulatory care and hospital emergency department of 1.3 in pain scores on a 0-10 visual analogue scale at 6 hours after presentation. A difference of 1.3 in pain scores has been used as a clinically important difference in other studies.^{9, 19} Data from the SCAPE trial provided an estimate of 3.2 for the standard deviation (SD) for pain scores and informed a conservative estimate of the correlation between baseline and 6-hour pain scores of 0.5¹⁸. The sample size allows for a conservative 15% dropout by 6 hours, informed by data from the SCAPE trial. It is anticipated that dropout will be minimised by potential use of an app to collect data including pain scores.

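### The pre-arrival opioid rule for time to first analgesia starts the clock 60 minutes after the ambulance dose whatever the arrival time, so recorded waits can be negative, shortened or inflated

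*Protocol*

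**What the plan says.** Section 6.4 lists time to first analgesia first among the secondary endpoints, "defined as time from presentation in ACU or ED to first dose of opioid analgesia administered". A bracketed exception follows. It covers a whole class of episodes ("For subjects given parenteral opioid prior to arrival in care unit, e.g. in ambulance"), and for these "timing will start from one hour after parenteral analgesia given in ambulance, even if subject presents less than one hour after" the ambulance dose.

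Nothing else in the protocol qualifies the exception. Section 9.5 leaves analgesia to local standard care ("This includes selection of analgesic drugs, doses and route of administration") and states no interval between an ambulance dose and the first dose on the unit. Section 9.4 places allocation before travel: "Randomization will be done over the phone when a pre-consented subject calls the local trial centre with symptoms of APC". Section 8 adds that the patient is then asked to attend the allocated location and that the trial is open.

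**The concern.** The general definition measures how long a patient waits after reaching the unit. The exception replaces that origin with a moment that does not depend on arrival. The first unit dose may come before that moment, and the moment itself may come before arrival. In the first case the recorded duration is negative. In the second, minutes before the patient reached the unit count as waiting there. Neither value is a time from presentation.

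The endpoint matters to the trial. The background section reports an observational comparison in which infusion-centre patients received parenteral medication substantially faster than ED patients, so the arms may well separate here. Ambulance use and pre-arrival opioid can also follow a known allocation, so the affected episodes need not be spread evenly between arms.

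**Working it through.** **Inputs.** From section 6.4: the general origin (presentation), the exception's origin (ambulance dose plus 60 minutes) and its scope (all subjects with pre-arrival parenteral opioid). From section 9.4: randomisation by phone. The protocol gives no ambulance-dose times, travel times, unit-dose times or share of pre-treated episodes, so all of these are assumed below. I take the end of the interval to be the first opioid dose on the unit. If the ambulance dose itself were counted as the first dose, every such episode would record A − (A + 60) = −60.

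**Formula.** Let A be the ambulance dose, P the arrival and U the first unit dose, in minutes.

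- Actual wait: W = U − P
- Recorded wait under the exception: R = U − (A + 60)
- Error: R − W = (P − A) − 60

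**Results with A = 0.**

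| Arrival P | Unit dose U | Actual W | Recorded R | Error |
|---|---|---|---|---|
| 10 | 40 | 30 | −20 | −50 |
| 20 | 50 | 30 | −10 | −40 |
| 20 | 80 | 60 | 20 | −40 |
| 60 | 90 | 30 | 30 | 0 |
| 90 | 105 | 15 | 45 | +30 |
| 120 | 140 | 20 | 80 | +60 |

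There are three cases:

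- R is negative whenever the unit dose falls within 60 minutes of the ambulance dose.
- R is positive but too short when arrival is within the hour and the unit dose comes after it.
- R includes pre-arrival minutes when arrival is more than 60 minutes after the dose.

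R equals W only when arrival is exactly 60 minutes after the dose.

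**A gentler reading.** Suppose the clock were meant to start at the later of P and A + 60. The added pre-arrival minutes would go, but P = 20, U = 50 would still give 50 − 60 = −10.

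**Possible effect on the comparison.** If the mean error e is the same in both arms, the ED-minus-ACU difference in means shifts by (share in ED − share in ACU) × e.

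- Shares 30% and 10%: 0.20 × (−40) = −8 minutes, or 0.20 × 30 = +6 minutes.
- Shares 20% and 5%: 0.15 × (−50) = −7.5 minutes, or 0.15 × 60 = +9 minutes.
- Shares 10% and 10%: 0 minutes.

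Equal shares do not make the negative values harmless. Suppose pre-treated patients in both arms have an ambulance dose 20 minutes before arrival, and unit doses come 15 minutes after arrival in one arm and 60 in the other. Recorded times are 35 − 60 = −25 and 80 − 60 = 20. The raw difference is still 45 minutes, but setting the negative value to zero leaves 20.

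**The plan's own figure.** No figure is stated for this endpoint. The stated figure, "The target sample size is 228 patient episodes (114 per group"), belongs to the pain score at 6 hours. With a difference of 1.3, SD 3.2, correlation 0.5, 90% power and two-sided α = 0.05, the adjusted SD is 3.2 × √(1 − 0.25) = 2.77. That gives 96 per arm, and 96 / 0.85 rounds up to 113, or 226 in total against 228 stated. It reproduces and does not depend on this clock.

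**The case against.** The exception has a sensible purpose. A patient who has just had parenteral opioid is not untreated, and timing from presentation may show a long wait for someone who already has analgesia on board. On this view the case of arrival within the hour and a later unit dose is what the rule was written for, and the shortened time is intended credit. That purpose is legitimate. The wording still does not achieve it: it covers every pre-arrival parenteral dose, not only recent ones, and it says nothing about unit doses given inside the hour.

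It can also be said that a statistical analysis plan could deal with negative values. It could, for instance by setting them to zero. But the protocol itself fixes the time origin, and an analysis plan would have to depart from section 6.4 to restore a time from presentation.

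Some stronger readings are not supported. A reader might infer that negative values break the planned analysis, but section 11.2 names no log-scale or survival model for this endpoint and defers the detail. A reader might also infer a bias of known size or direction. The documents give no shares or times, errors of opposite sign partly cancel, and equal shares with equal mean errors shift the means by zero. Finally, one might want to adjust for pre-arrival opioid or leave those episodes out. Because that treatment can follow open allocation, conditioning on it could itself bias the comparison, and exclusion departs from the intention-to-treat basis in section 11.2.

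**Conclusion.** The rule as written is inconsistent with the endpoint it modifies. For an episode with pre-arrival parenteral opioid it misstates the wait by (arrival minus ambulance dose) minus 60 minutes, which can produce a negative, a shortened or an inflated time. This follows from the wording alone and needs no assumption beyond the end point being the first unit dose.

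It does not follow that every such episode is negative or inflated, or that the treatment comparison is biased by a particular amount. The shifts of −8 to +9 minutes shown above rest on assumed shares and on one common error for all pre-treated episodes. The defect is confined to one secondary endpoint and to an unknown number of episodes. It is worth correcting because the correction is cheap and the endpoint is one on which the arms are likely to differ.

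**What to change.** In section 6.4, define the main analysis of time to first analgesia as minutes from presentation to the first opioid dose on the unit, for every randomised episode, and delete the one-hour offset. Record pre-arrival parenteral opioid (yes or no, and its time) and report it descriptively by arm. Do not adjust for it or exclude on it in the main analysis.

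If the sponsor wants to credit pre-arrival analgesia, add a sensitivity analysis with the clock starting at the later of presentation and ambulance dose plus 60 minutes, counting unit doses before that point as zero. The zero rule can compress a real difference (45 to 20 minutes in the example above), which is why it should not be the main analysis.

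The cost is one amended sentence. The current rule already requires the ambulance-dose time, so no new data are needed. The downside is small: pre-treated patients who arrive within the hour will show a longer wait than under the present rule. The change concerns only how the outcome is timed and implies nothing about when analgesia should be given.
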